5.4 Safety Evaluation

The safety of the LS301 will be assessed by closely monitoring the patients' vital signs and laboratory tests as described below.

5.4.1 Vital Signs

All vital signs will be recorded on the case report form. Vital signs may be obtained with the subject in the supine or upright position. Care will be taken to obtain subsequent recordings with the subject in the same position (supine or upright). Although allergic or other immediate adverse reactions are not anticipated, subjects will be monitored for at least 60 minutes post injection in an area where emergency equipment is available. Vital signs will be obtained pre-injection (within 30 minutes prior to injection of LS301), within 30 minutes post injection, at 60 minutes post injection, and prior to surgery. Vital signs will include the following: heart rate, systolic blood pressure, diastolic blood pressure, respiratory rate, and body temperature. The following changes from baseline will be considered noteworthy:

- Heart rate > 20 beats per minute
- Systolic blood pressure > 20 mm Hg
- Diastolic blood pressure > 10 mm Hg

Noteworthy changes will be documented on the CRF, and they will be marked as clinically significant or not. If clinically significant, the principal investigator will assess the causality of the change to the injection of LS301. Clinically significant changes in vital signs will be followed up hourly until they return to baseline or normal levels, or until follow-up is no longer warranted. If a clinically significant change of a vital sign is noted, it will be reported on the adverse event log.

5.4.2 Clinical Laboratory Testing

Laboratory tests will consist of the following: standard CBC, comprehensive metabolic panel and urinalysis obtained at the following time points:

- Baseline: within 30 minutes prior to injection of LS301
- 60 minutes after injection of LS301
- Approximately one hour prior to surgery

Approximately 14 ml of blood and a urine sample will be collected at each time point. For patients enrolled in phase 1B and phase 2 of the study, a portion of the blood samples from each time point will be used to identify the predominant blood protein(s) that binds LS301 and mediates the bioavailability of the agent (refer to Section 5.6). Phase 1B refers to phase 1 study after completing drug safety and selecting optimal dose for testing at 2 and 4 hours from injection to surgery. The current project is that if 3 patients at each of the 3 dose level do not experience adverse events, we will need only 9 patients for the drug safety study (phase 1A) and additional 9 patients at the selected dose for testing at 2, 4, and >12 hours (3 patients for each time point) from injection to surgery.

The results of standard of care laboratory testing obtained up to 30 days post injection will be reviewed. Analysis of this will take into account that the subject has undergone surgical removal of tumor and neoadjuvant treatment including hormonal therapy or chemotherapy.

The following changes from baseline clinical laboratory values are considered to be noteworthy and require assessment as to clinical significance when they fall outside of normal limits. Clinically significant changes in laboratory values should be followed up daily until they return to baseline or normal levels, or until follow-up is no longer warranted. Laboratory values that are abnormal at baseline but move into normal range will not be considered clinically significant. If a clinically significant change of a laboratory value is noted, it will be reported on the AE log.

Analyte	Change from baseline
Hemoglobin	> 2g/dL
WBCs	> 1 K/mm ³
Neutrophils	> 10 %
Lymphocytes	> 10%
Platelets	> 50 K/mm ³
Creatinine	> 0.75 mg/dL
BUN	> 20 mg/dL
Calcium	> 1mg/dL
Sodium	> 5 mmol/L
Potassium	> 0.5 mmol/L
CO ₂	> 4 mmol/L
ALT (SGPT)	> 150 IU/L
AST (SGOT)	> 100 IU/L
Alkaline Phosphatase	> 150 IU/L
Total Bilirubin	> 0.5 mg/dL
Albumin	> 1g/dL

Changes in pre and post injection urinalysis will be noted but due to variability will not be used to determine clinical significance for changes due to the injection of LS301.

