After phase 1 data has been submitted to and discussed with the FDA, an additional cohort of 88 patients will be enrolled to the phase 2 portion of the trial to assess the diagnostic capabilities of LS301 for identification of positive margins at surgery. Based on preclinical studies^{36,37,40,43,68}, the anticipated optimal dose for LS301 is 0.1 mg/kg body weight (BW). This dose is a fraction of ICG concentration currently approved for human use. LS301 will be formulated in 1% human serum albumin (HSA) in saline and administered intravenously as a slow infusion over 5-10 minutes. Based on LS301 in 1% HSA and assuming a 60 kg adult with 1.6 m² surface area and using the conversion factor $k_m = 60/1.6 = 37 \text{ kg/m}^2$, the equivalent dose is $100 \mu\text{g/kg} \times 37 \text{ kg/m}^2 = 3.7 \text{ mg/m}^2$.

In all patients, LS301 will be administered 4-24 hours before lumpectomy. LS301 uptake in primary breast cancer or SLN versus uninvolved tissue will be visualized with the CVG system during surgery by a member (operating or non-operating) of the surgical team. The NIR light source for the CVG is based on light-emitting diodes (LEDs) or laser light operating at 15-20 mW/cm² output at tissue, which can deliver sufficient light to biological tissues and induce fluorescence emission to meet the needs of the planned clinical studies. It should be noted that the light source is below the US FDA recommended limit for NIR exposure and ANSI standard. The fluorescence signals will be received by the detector portion of our device. Gain-settings could be easily adjusted during operation to optimize the contrast between high fluorescence areas (tumors) and low fluorescence areas (normal tissues). Real-time fluorescence image will be displayed in the goggle eyepiece as well as on a secondary monitor to facilitate viewing by other members of the surgical team in the OR. Images from the CVG or SPY will not be used to alter the surgical plan in any way.

Fluorescence in the excised tissue at the margins will be determined by quantitative near-infrared fluorescence microscopy. For each patient, at least 4 specimens from excised tissue will be analyzed, including suspected tumor and suspected healthy tissue. De-identified data will be stored on a computer. Stored information will only have coded numbers and not the names of the patients to ensure patient privacy.

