5.0 STUDY PROCEDURES

5.1 LS301 Preparation

LS301 will be prepared under cGMP protocol and supplied in an amber-colored vial as a lyophilized product in 1% HSA/PBS aqueous solution. Each vial will contain 2 mg LS301. Before administration, 10 mL of PBS will be added to the lyophilized powder and mixed by shaking for 1 minute. The aqueous formulation is stable at room temperature for 4 hours or in the refrigerator (2-8°C) for 24 hours. The agent will be administered 4-24 hours before surgery.

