5.2 Procedures

5.2.1 Phase 1

A rolling six design (refer to Section 8.1) will be used to enroll patients who are being treated for pathologically proven breast cancer prior to definitive surgical interventions in the phase 1A dose escalating portion of the study, during which LS301 will be administered intravenously at one of three doses (see table below). Patients will be observed for dose-limiting toxicities (DLT) (refer to Section 5.2.1.3).

LS301 Dose Level	LS301 Dose
Level 1 (starting dose)	0.05 mg/kg
Level 2	0.075 mg/kg
Level 3	0.1 mg/kg

The patient will undergo surgery 4-24 hours after administration of LS301 using current best practices. Breast tissue and axillary LNs will be imaged non-invasively prior to start of surgery and excised breast tissue and SLNs will be examined ex vivo for the presence of LS301 fluorescence using our Cancer Vision Goggles (CVG) to determine if LS301 accumulated in the breast cancer. We will quantify fluorescence intensity in the cancer to establish the feasibility of observing LS301 fluorescence with the imaging system.

The dose used in cohort 1 is the lowest dose (0.05mg/kg) and was used exclusively for safety assessment. The investigators did not expect to detect LS301-associated tumor tissue fluorescence before incision at this lowest dose level. Therefore, cohort 1 patients will not be imaged non-invasively to assess tumor tissue fluorescence before incision. Non-invasive tumor fluorescence examination will be initiated from cohort 2 onwards, where higher doses will be used.

Investigators do not expect the 1st dose (0.05 mg/kg) or 2nd dose (0.075 mg/kg) to lead to any detectable fluorescence non-invasively in the axilla before sentinel lymph node excision due to the low concentration of expected LS301 retention in lymph nodes. Therefore, lymph node fluorescence will not be assessed non-invasively before incision for cohorts 1 and 2. Investigators will plan to image lymph node regions non-invasively starting with cohort 3 due to the higher injected dose (0.1 mg/kg).

After the optimal dose has been determined, an additional 9 patients will be enrolled in the phase 1 expansion cohort to evaluate for safety. This expansion cohort is considered phase 1B and will be conducted at UT Southwestern Medical Center.

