5.2.3 Administration of LS301

The patient will undergo intravenous injection of LS301 4-24 hours prior to surgery. A study nurse or other qualified member of the study team will inject the LS301 via IV over 5-10 minutes in the office or pre-op room (as applicable) and will monitor the patient as described in Section 5.4 below. Administration of LS301 will not interfere with the standard of care, including all standard of care for lymph node assessment using ^{99m}Tc Tilmanocept injection on the day of or day before surgery.

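### Phase 1B includes a 2-hour injection-to-surgery group (3 of 9 patients), but the rest of the protocol sets a 4-24 hour window with no exception

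*Combined protocol and SAP*

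**What the plan says.** **The timing groups.** Section 5.4.2, on laboratory testing, is the only place where phase 1B is given injection-to-surgery groups. One sentence describes phase 1B as following completion of drug safety and "selecting optimal dose for testing at 2 and 4 hours from injection to surgery". The next projects an "additional 9 patients at the selected dose for testing at 2, 4, and >12 hours (3 patients for each time point", with each time again counted up to surgery. The first sentence has two time points and the second has three.

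**The window.** Section 1.10 states: "In all patients, LS301 will be administered 4-24 hours before lumpectomy". Section 5.1 states: "The agent will be administered 4-24 hours before surgery". Section 5.2.3 states: "The patient will undergo intravenous injection of LS301 4-24 hours prior to surgery". Section 5.2.1 repeats the same window for surgery in phase 1, and that section also introduces phase 1B. None of the four makes an exception for phase 1B.

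**The same nine patients elsewhere.** Section 5.2.1 says that "an additional 9 patients will be enrolled in the phase 1 expansion cohort to evaluate for safety". Section 8.1 says the nine will be tested at the MTD, with an optimal imaging dose then recommended. Section 8.4 treats them as one group in its DLT probability table. None of these sections mentions timing groups, and sections 8.2 and 8.3 contain no endpoint or comparison by interval.

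**Blood draws.** Sections 5.4.2, 5.4.4 and 5.6.1 share one schedule: baseline, 60 minutes after injection, and an hour before surgery (5.4.2 makes this last time approximate). Section 5.4.4 uses these samples to determine the half-life of LS301.

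**The concern.** Two instructions govern the same patients and cannot both be followed. A patient operated on 2 hours after injection breaches the window in four sections. Moving that patient to 4 hours or later departs from 5.4.2. Because 5.4.2 also disagrees with itself, staff cannot tell whether two groups or three are intended.

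Two further consequences follow. The common blood schedule was not adapted to a 2-hour interval, which affects the half-life estimate. And if the groups exist to learn about timing, the plan does not say what will be done with the result, although phase 2 is expected to use the phase 1 procedures (5.2.2).

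**Working it through.** **Step 1: is the 2-hour group a stray line?** Three time points × 3 patients = 9, which matches the expansion cohort size in 1.10, 5.2.1, 8.1 and 8.4. The 2-hour interval also appears in both sentences of 5.4.2. It reads as an intended sub-design that was not carried into the procedures or the statistical section.

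**Step 2: compare each group with the 4-24 hour window.**

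| Group in 5.4.2 | Patients | Against 4-24 hours |
|---|---|---|
| 2 hours | 3 | Outside (2 < 4) |
| 4 hours | 3 | Inside, on the lower limit |
| >12 hours | 3 | Inside if surgery is by 24 hours; 5.4.2 states no upper limit |

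Share necessarily outside the window: 3/9 = 33%.

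**Step 3: nominal post-dose draw times.** For surgery T hours after injection, the draws fall at 1 hour and at T − 1 hours.

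| T (hours) | First post-dose draw (hours) | Second post-dose draw (hours) | Gap (hours) |
|---|---|---|---|
| 2 | 1 | 1 | 0 |
| 4 | 1 | 3 | 2 |
| 12 | 1 | 11 | 10 |
| 24 | 1 | 23 | 22 |

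Assume one-phase exponential decline, the model used for the dog data in 1.8.2. With concentrations C1 and C2 at times t1 and t2, the half-life is ln 2 × (t2 − t1) / ln(C1/C2). The baseline sample precedes the dose and adds no information on decline. At T = 2 the nominal gap t2 − t1 is zero, so a single patient's half-life cannot be estimated. In practice the pre-surgery draw is approximate, so the two samples could be a few minutes apart, which is still too close to be useful.

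**Step 4: what does not depend on the interval.** The exact binomial probability of 3 or more DLTs among 9 reproduces the table in 8.4:

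| True DLT rate | Stated | Recomputed |
|---|---|---|
| 5% | 0.0084 | 0.0084 |
| 10% | 0.053 | 0.0530 |
| 20% | 0.262 | 0.2618 |
| 50% | 0.91 | 0.9102 |

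The table uses only the number of patients and the DLT rate. DLTs are assessed in the hour after injection (5.2.1.3, 5.3), which ends before surgery even at 2 hours. The phase 2 power calculation for 88 patients does not use the interval either.

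**The case against.** The strongest reply is that this is loosely worded planning text with little consequence. The sentence in 5.4.2 is a projection that depends on phase 1A running without adverse events. The DLT table and phase 2 power are untouched, a safety expansion and timing subgroups can coexist, and 5.2.2 allows protocol revisions based on phase 1 data before phase 2 opens.

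Much of this stands, and it rules out several stronger readings that a reader might infer:

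- *That timing could not be studied at all.* The 4-hour and >12-hour groups, 6 of the 9 patients, can run inside the window. Only the 2-hour group conflicts.
- *That 6 of 9 patients breach the window.* A time beyond 12 hours is compatible with the 24-hour limit, and no text plans surgery later than that. The missing upper limit is a gap, not a breach.
- *That acute safety monitoring is lost at 2 hours.* The 60-minute sample is still taken, as are vital signs before surgery (5.4.1), and standard-of-care laboratory results up to 30 days are reviewed. What is lost is a distinct later draw in three patients.
- *That two time points would mean larger groups.* The documents give no such split; the only stated allocation is 3 per time point.
- *That 8.1 calls the cohort a safety expansion.* Section 5.2.1 does. Section 8.1 speaks of testing at the MTD and recommending an imaging dose.

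The reply does not remove the conflict. The cohort of nine is stated without condition in other sections, and the 2-hour group has no written exemption. The revision route in 5.2.2 comes after phase 1B, too late for scheduling those patients, and supplies no criterion for using the timing data.

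**Conclusion.** The inconsistency is real and should be corrected. Three of nine planned phase 1B patients (33%) are assigned an interval that four other sections do not allow, and 5.4.2 is also inconsistent about the number of groups. For those three patients the nominal blood schedule leaves about one distinct post-dose laboratory and LS301 concentration time, which does not support a within-patient half-life.

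The 3-of-9 figure assumes the three-group allocation in 5.4.2. The coincidence of draws assumes nominal timing, and the half-life argument assumes one-phase decline. The effect is confined to phase 1B scheduling, the half-life data and the unstated use of the timing results. It does not reach the one-hour DLT assessment or the phase 2 sample size. Which interval is right is for the clinical team and is not judged here.

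**What to change.** 1. Reconcile 5.4.2 with 1.10, 5.1, 5.2.1, 5.2.3 and 8.1 so that one set of phase 1B injection-to-surgery intervals, chosen by the clinical team, applies throughout. State the number of groups, the patients in each, and both limits of any open-ended interval.
2. Make the blood-draw times in 5.4.2, 5.4.4 and 5.6.1 consistent with those intervals, and say how the half-life will be estimated if some patients have only one distinct post-dose time.
3. State in 8.1 or 8.3 how results by interval will be summarised and how they will be used to set or keep the phase 2 window. With three patients per group a descriptive summary is realistic.

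The cost is amendment wording. The cohort size of nine, the DLT table and the phase 2 sample size need no change. The conflict should be settled before phase 1B patients are scheduled.

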5.2.1.1 Dose Escalation Schema

LS301 Dose Level	LS301 Dose
Level 1 (starting dose)	0.05 mg/kg
Level 2	0.075 mg/kg
Level 3	0.1 mg/kg

Dose escalation may occur as soon as the last patient in a cohort has completed her one-hour post-injection toxicity monitoring.

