5.2.1.3 Definition of Dose-Limiting Toxicities

DLT is defined as any grade 2 or above toxicity that occurs during the hour after injection that is considered possibly, probably, or definitely related to LS301.

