5.3 Evaluability

All patients who receive an LS301 injection are evaluable for toxicity. Patients are evaluated from time of injection to one-hour post-injection.

Patients enrolled in phase 1 are evaluable for DLT assessment during the hour after injection. Patients in phase 2 will not be assessed for DLT.

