5.5 Risks and Adverse Event Monitoring

A potential risk specific to this experiment procedure is the injection of LS301. The imaging agent is not known to cause any serious adverse events in preclinical models. However, it is possible that some patients may experience mild reactions similar to those they might experience related to OctreoScan (a nuclear (SPECT) imaging agent) such as dizziness, fever, changes in liver enzymes, and nausea. The dose escalation procedure will allow us to monitor these reactions from low to high doses of LS301. There are other experimental tumor targeted imaging agents currently being evaluated in human patients (see the table below). Most of them either user antibodies tagged with ICG or dye-labeled biomolecule.

List of imaging agents under clinical investigation for image-guided surgery

Sl no	Agent	Clinical Trial	Trial type	Cancer type	Adverse reactions
1	Cetuximab IRDye800	NCT01987375	Phase 1 dose escalation study	Head and neck	Yes, in humans ⁶⁹ and monkeys ⁷⁰
2	Panitumumab IRDye 800	NCT02415881	Phase 1 safety/efficacy study	Head and neck	No reports found
3	Bevacizumab-800CW	NCT01508572 NCT02583568	Phase 1 Phase 2	Breast	No reports found. None reported for PET version ⁷¹
4	ICG and goggle	NCT02316795	Pilot	Breast and Melanoma	None reported ⁴³
5	ICG and Fluobeam	NCT01738217	Phase 1 and Phase 2	Liver	No reports found
6	BLZ 100 and Fluobeam	NCT02097875	Phase 1 dose escalation	Skin cancer	None in humans ⁷² and dogs ⁷³
7	BLZ 100 and unspecified system	NCT02234297	Phase 1 safety	Glioma	None in humans ⁷² and dogs ⁷³

The risks from the CVG system are extremely low. The system does not come into contact with the test subject. It utilizes safe invisible NIR light between 700 and 900 nm at a very low fluence rate ($\leq 25 \text{ mW/cm}^2$). This imaging system meets the US FDA definition of a “non-significant risk” device, and indeed could be considered “equivalent” to the Spy™ system, which has already obtained US FDA approval as a non-significant risk device.

The US FDA limit for NIR exposure is 10,000 mW/cm² and the current system utilizes 2.5-25 mW/cm² for a total duration of less than 30 minutes in the initial imaging and 10 minutes per subsequent imaging segments. This is equivalent to the current NIR dose emitted from the standard 5-lantern surgical lights commonly used in the operating room.

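### Dose escalation may open before the last patient's 60-minute laboratory results, the only post-injection ones inside the DLT window, are known

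*Combined protocol and SAP*

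**What the plan says.** Section 5.2.1.3 sets the DLT window: "DLT is defined as any grade 2 or above toxicity that occurs during the hour after injection", provided the toxicity is at least possibly related to LS301. Section 5.3 uses the same hour for evaluability: "Patients are evaluated from time of injection to one-hour post-injection".

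Section 5.4.2 schedules blood and urine tests at three times: baseline, "60 minutes after injection of LS301", and roughly one hour before surgery. On what follows from an abnormal value it says: "If a clinically significant change of a laboratory value is noted, it will be reported on the AE log". It does not say when the results must be read in relation to a dose decision.

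Section 5.2.1.1 sets the earliest time for a dose increase: "Dose escalation may occur as soon as the last patient in a cohort has completed her one-hour post-injection toxicity monitoring".

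Section 8.1 gives the decision rule. Escalation needs 3/3, 4/4, 5/5, 5/6 or 6/6 patients evaluated without a DLT, and two or more DLTs at a level lead to de-escalation. Once six patients are in, enrolment pauses until at least five have completed without a DLT in the evaluation period.

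**The concern.** The sample that could reveal a laboratory DLT is taken at the moment when the protocol first permits escalation. A blood count and metabolic panel drawn at 60 minutes cannot already have been reported and graded at 60 minutes. Read literally, the rule lets the DLT count for a cohort close with the last patient's laboratory status unknown.

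The decisions exposed are the two dose increases, from 0.05 to 0.075 mg/kg and from 0.075 to 0.1 mg/kg, in a first-in-human study. A late result is not lost. It can still be counted when it arrives, but by then a patient may already have been given the higher dose.

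A later sample might not show the same change. Surgery follows injection by 4 to 24 hours, so the next draw falls about 3 to 23 hours after injection. Section 1.8.2 reports that one of three dogs had a fall in neutrophils at 5 to 60 minutes that had recovered by 4 hours. That example is limited. The dose of 0.9 mg/kg was 9 to 18 times the trial doses by mg/kg (0.9/0.1 and 0.9/0.05), the fall was presumed idiosyncratic, and no grade is given. It shows that a short-lived laboratory-only change is possible. It does not show that one is likely in patients.

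**Working it through.** **Step 1: the sequence in time (phase 1A).**

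| Time after injection | What happens | Section |
|---|---|---|
| 0 to 60 min | DLT and toxicity window | 5.2.1.3, 5.3 |
| 5–10 min and 60 min | ECG | 5.4.3 |
| within 30 min and 60 min | Vital signs | 5.4.1 |
| 60 min | Only post-injection laboratory draw in the window | 5.4.2 |
| end of one-hour monitoring | Escalation permitted | 5.2.1.1 |
| about 3 to 23 h | Next laboratory draw | 5.2.1, 5.4.2 |

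Vital signs and ECG have an earlier reading inside the window. Only laboratory values depend on a single sample at its very end.

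**Step 2: check of the plan's own DLT figures.** The only DLT probabilities in the plan are in the section 8.4 table for the nine-patient expansion cohort, P(X ≥ 3) with n = 9. The exact binomial gives 0.00836 at 5% (printed 0.0084), 0.2618 at 20% (0.262) and 0.9102 at 50% (0.91). The 1% row is 0.000080 against a printed 0.000084, which is immaterial. The table reproduces, but it does not address escalation.

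**Step 3: how often one missed DLT in the last patient would matter.** Let p be the true DLT rate, the same and independent for each patient. Assume that only the last patient's results are pending and that a DLT in that patient goes uncounted.

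- *Cohort of six.* The miss is decisive when the last patient has a DLT and exactly one of the other five does. The record then shows 5/6 DLT-free (escalate) when the truth is two DLTs (de-escalate). Probability: p × 5p(1−p)⁴ = 5p²(1−p)⁴. This is one third of P(exactly 2 of 6) = 15p²(1−p)⁴.
- *Cohort of three*, the case that section 5.4.2 projects. The miss turns 2/3 DLT-free, which is not an escalation outcome, into 3/3. Probability: p(1−p)². Full counting would have taken the cohort on to six and blocked escalation only if at least one of the next three also had a DLT: p(1−p)² × [1−(1−p)³].

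At p = 0.05:
- six patients: 5 × 0.0025 × 0.8145 = 0.0102;
- three patients: 0.05 × 0.9025 = 0.0451, and 0.0451 × 0.1426 = 0.0064.

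| True DLT rate | Six patients, decisive | Three patients, 2/3 read as 3/3 | Three patients, escalation that would have been blocked |
|---|---|---|---|
| 1% | 0.05% | 0.98% | 0.03% |
| 5% | 1.0% | 4.5% | 0.6% |
| 10% | 3.3% | 8.1% | 2.2% |
| 20% | 8.2% | 12.8% | 6.2% |

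**Step 4: why these are upper bounds.** Each figure has still to be multiplied by the chance that the DLT shows only in laboratory values and that its result arrives after the decision. The documents give neither, so the actual rate cannot be computed.

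**The case against.** The best reply is that the protocol defines monitoring by its content and not by the clock. Section 5.2.3 has staff monitor the patient as section 5.4 describes, section 5.5 says the same, and section 5.4 opens by naming laboratory tests as part of safety monitoring. On that reading, one-hour monitoring is not complete without the 60-minute laboratory test. Section 8.1 also asks for patients evaluated without a DLT, and the escalation sentence is permissive. Much of this stands: the sample must have been drawn, and the protocol does not direct anyone to escalate without results. But drawing a sample is not the same as having its result, section 5.3 ends evaluation at one hour, and no sentence makes escalation wait. The reply shows that a careful team would probably wait. It does not show that the rule requires it.

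A reader might also infer something stronger: that the clinical-significance mark in section 5.4 removes grade 2 changes from the DLT count. The documents do not support that. The laboratory sentence quoted from section 5.4.2 and the vital-sign sentence in section 5.4.1 ("If clinically significant, the principal investigator will assess the causality of the change to the injection of LS301") say what happens if a change is significant, not only if. Any related grade 2 toxicity still counts under section 5.2.1.3. Section 5.7.1 captures all adverse events, and section 8.2.1 and Appendix A apply CTCAE version 5.0.

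Similarly, temperature and respiratory rate are measured but have no noteworthy criterion, although section 5.5 lists fever as a possible reaction. A fever is still reportable under section 5.7.1. Grading every value regardless of clinical judgement is also debatable. Section 1.8.2 describes apparent creatinine rises in all three dogs that probably reflected LS301 interfering with the assay. These matters are clarifications or design preferences and form no part of this point.

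**Conclusion.** The timing gap holds, and it is minor. As written, the escalation rule allows the next dose level to open while a laboratory-only DLT in the last patient is still unknown.

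Section 8.5 expects no toxicity, so the 1% to 5% rows are the most relevant. There the bound is at most about 1% of six-patient cohorts, and at most about 0.6% of three-patient cohorts for an escalation that full counting would have blocked. At a 20% DLT rate the bounds are 8.2% and 6.2%.

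These figures assume independent patients with a common rate and only the last patient's results pending. If patients were injected close together and the one missed DLT could be in any of them, the figures would be three times as large: 3.1% for six patients and 1.9% for three at a 5% rate. Symptomatic reactions within the hour are not affected, and neither is any phase 2 result.

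**What to change.** In sections 5.2.1.1 and 8.1, state that escalation may occur only after the 60-minute laboratory results of all patients in the cohort have been received, reviewed and assessed against the DLT definition in section 5.2.1.3.

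This needs no new sample, visit or patient. The cost is one sentence in each section and a short delay before each of the two possible dose increases, set by the laboratory's turnaround time, which the documents do not give.
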